### 1.2 OBJECTIVES

#### 1.2.1 Primary objectives

The primary objective of this study is to evaluate long term skeletal response to eliglustat in adult patients who successfully completed one of the Phase 2 or Phase 3 studies.

#### 1.2.2 Secondary objectives

The secondary objectives are to evaluate:

- The safety of eliglustat by (S)AE continuous monitoring,
- The quality of life by Short Form-36 Health Survey and
- Biomarkers of GD1 (chitotriosidase, plasma GL-1 and lyso-GL-1).

### 1.3 DETERMINATION OF SAMPLE SIZE

This study will enroll all eligible patients having completed one of the Phase 2 or Phase 3 trials (approximately 32 patients).

This is a long term extension study. No sample size calculation has been performed. The patients who will be enrolled have already been receiving the IMP for approximately 4 to 8 years prior to the start of the study. The aim of the study is to continue collecting long term data on the efficacy and safety of the IMP.

### 1.4 STUDY PLAN

This is an open label, interventional, non-comparative, multicenter, multinational Phase 3b study to evaluate long term skeletal responses to eliglustat, eliglustat safety and effect on quality of life in adult patients who successfully completed one of the Phase 2 or Phase 3 studies in the eliglustat program.

The study includes a screening period from Day -45 to Day -1 and a long-term treatment period from Day 1 to the end of study. The duration of study participation for individual patients will be at least 2 years (unless early discontinuation occurs) and up to 4 years, or until commercial eliglustat is available to patients through reimbursement.

Analysis will be performed on safety and efficacy endpoints at 2 points in this study:

- After the last patient enrolled has completed 2 years of treatment (two-year analysis period)
- At the study completion

**Table 1 - Study schedule**

Variable	Visit schedule
Gaucher disease clinical assessment (mobility, bone crisis and bone pain)	Screening, every 52 weeks (yearly) until end of study visit
X-ray femurs and lumbar spine	Screening, every 104 weeks (every 2 years) until end of study visit
DXA (hip and lumbar spine)	Screening, every 52 weeks (yearly) until end of study visit
MRI (entire bilateral femur and lumbar spine, Spleen and liver volume)	Screening, every 52 weeks (yearly) until end of study visit
QOL questionnaire (SF36)	Screening, every 26 weeks (every half year) until end of study visit
Hematology (including HGB and PLAT)	Screening, every 26 weeks (every half year) until end of study visit
Serum chemistry (AST, ALT, AP, Total bilirubin, albumin, GGT)	Screening

## **1.5 MODIFICATIONS TO THE STATISTICAL SECTION OF THE PROTOCOL**

Not applicable.

## **1.6 STATISTICAL MODIFICATIONS MADE IN THE STATISTICAL ANALYSIS PLAN**

The definition for treatment-emergent period was added for clarification, specifying the on-treatment period and residual treatment periods, respectively in [Section 2.1.4](#).

## 2 STATISTICAL AND ANALYTICAL PROCEDURES

### 2.1 ANALYSIS ENDPOINTS

#### 2.1.1 Demographic and baseline characteristics

The baseline is referred to study baseline, which is defined as available assessment result or status before the first dose of eliglustat in this study.

All baseline safety and efficacy parameters are presented along with the on-treatment summary statistics in the safety and efficacy sections ([Section 2.4.5](#) and [Section 2.4.4](#)).

##### *Demographic characteristics*

Demographic variables are gender (Male, Female), race (Caucasian/white, Black, Asian/Oriental, American Indian or Alaska Native, Native Hawaiian or other Pacific Island, other), Jewish Descent (Jewish Ashkenazi, Jewish Sephardic, Non-Jewish), age at study entry in years (quantitative), ethnicity (Hispanic/Latino, non-Hispanic/Latino).

##### *Medical or surgical history*

Medical (or surgical) history will be completed according to the protocol.

This information will be coded using the version of Medical Dictionary for Regulatory Activities (MedDRA) currently in effect at Sanofi at the time of database.

Medical (or surgical) history recorded in the previous study will not be re-entered as medical (or surgical) history in this study, but will be used in the analysis of this study.

##### *Disease characteristics at baseline*

Specific disease history includes the following:

- Time since initial Gaucher diagnosis relative to enrollment (in years)
- Time since first symptoms of Gaucher relative to enrollment (in years)
- CYP2D6 metabolizer status (poor, intermediate, extensive, ultra-rapid)

##### *Vital signs*

Vital signs at baseline are height at study entry (quantitative), weight at study entry (quantitative) and BMI at study entry (quantitative).

Any technical details related to computation, dates, and imputation for missing dates are described in [Section 2.5](#).

## 2.1.2 Prior or concomitant medications

All medications taken within 30 days prior to patient providing written, informed consent to the study until the end of the study, including eliglustat if the last dose of eliglustat in the previous study happened in this period of time, are to be reported in the case report form pages. Enzyme replacement treatment (ERT) should also be included if the patient was on ERT during the period between the end of the previous study and the screening visit.

All medications will be coded using the World Health Organization-Drug Dictionary (WHO-DD) using the version currently in effect at Sanofi at the time of database lock.

- Prior medications are all ongoing medications at the time of screening, and medications received during the 30 day period prior to screening even if no longer taken at the time of screening, including eliglustat and enzyme replacement therapy (ERT). Prior medications can be discontinued before first administration or can be ongoing during treatment phase.
- Concomitant medications are any treatments received by the patient concomitantly with eliglustat, during the on-treatment period. A given medication can be classified both as a prior medication and as a concomitant medication. Concomitant medications do not include medications started after the on-treatment period (as defined in the observation period in [Section 2.1.4](#)).

Any technical details related to computation, dates, imputation for missing dates are described in [Section 2.5](#).

## 2.1.3 Efficacy endpoints

The detailed assessment schedule refers to [Table 1](#) in [Section 1.4](#). No imputation will be conduct for all the endpoints.

### 2.1.3.1 Primary efficacy endpoint(s)

Five common skeletal manifestations of Gaucher disease will be assessed:

- Mobility, bone pain and bone crisis, as assessed by the Gaucher Disease clinical assessments;
- Bone marrow infiltration;
- BMD;
- Lytic lesions, osteonecrosis, fractures and infarcts;
- Bone biomarkers.

#### **2.1.3.1.1 Gaucher disease clinical assessments (mobility, bone pain, bone crisis)**

Patients will be asked to rate mobility and bone pain as below:

- Current mobility
  - Unrestricted mobility
  - Walks with difficulty
  - Walks with orthopedic aid
  - Requires wheelchair
  - Bedridden
- Level of bone pain during the last 4 weeks as
  - None
  - Very mild
  - Mild
  - Moderate
  - Severe
  - Extreme

In addition, investigators will report the number of bone crisis since the previous assessment. Bone crisis is defined as pain with acute onset, which requires immobilization of the affected area, narcotics for relief of pain, and may be accompanied by one or more of the following: periosteal elevation, elevated white blood cell count, fever, or debilitation of >3 days. Category of number of bone crisis defined as:

- No bone crisis
- 1 – 2 bone crisis
- >2 bone crisis

Gaucher disease clinical assessments will be performed at screening and then yearly.

#### **2.1.3.1.2 Bone marrow infiltration**

The assessment of bone marrow infiltration is based on the sum of seven bone marrow burden scores for spine (T1-weighted, T2-weighted, infiltration pattern and fat in basivertebral region) and femur (T1-weighted, T2-weighted, and sites of involvement) assessed by MRI views. BMB scores range from 0 to 16 and will only be calculated for patients who have non-missing values for all seven scores.

The BMB score for this study will be assessed by two readers. The primary readers will read in pairs, blinded to patient, treatment, and time point. If readers differ by a score of one or more, for each of the questions, for the femur subtotal, for the spine subtotal and for the overall score, a third reader will serve as the adjudicator and will provide a third read. The average of the three reader results will be used in the analysis. Bone marrow infiltration will be measured at screening and then yearly.

Bone MRI will be read locally and centrally. The central reads will be used for analysis.

Lumbar Spine:

T1-weighted:

0 = Slightly hyperintense  
1 = Isointense  
2 = Slightly hypointense  
3 = Hypointense  
NA = Not assessable

T2-weighted:

0 = Isointense  
1 = Slightly hypointense  
1 = Slightly hyperintense  
2 = Hypointense  
2 = Hyperintense  
NA = Not assessable

Infiltration Pattern:

0 = None  
1 = Patchy  
2 = Diffuse

Fat in basivertebral vein region

0 = Preservation of fat  
1 = Absence of fat  
NA = Not assessable

Femur:

T1-weighted:

0 = Slightly hyperintense or isointense  
1 = Slightly hypointense  
2 = Hypointense  
NA = Not assessable

T2-weighted:

0 = Isointense  
1 = Slightly hypointense  
1 = Slightly hyperintense  
2 = Hypointense  
2 = Hyperintense  
3 = Mixed type  
NA = Not assessable

Sites of Involvement:

0 = No site involvement  
1 = Diaphysis  
2 = Proximal epiphysis / apophysis  
3 = Distal epiphysis  
NA = Not assessable

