In vitro, eliglustat is a substrate of the efflux transporter P glycoprotein (P-gp). In addition, CYP2D6 and to a lesser degree cytochrome P450 3A4 (CYP3A4) are involved in eliglustat metabolism in vitro. Consequently, moderate and strong inhibitors of CYP2D6 and CYP3A increase its exposure, and potent cytochrome P450 3A (CYP3A) inducers decrease it. In addition, mild QTc interval prolongation is predicted to occur in a dose proportional fashion at eliglustat plasma concentrations beyond the therapeutic range. For these reasons, the restrictions on concomitant medications shown in [Table 1](#) (Concomitant Medications Recommendations for Use with Eliglustat) have been proposed in product labeling for eliglustat. These restrictions will help ensure that exposure to eliglustat will remain within the range shown to be safe and effective in the clinical studies.

Previous clinical studies of eliglustat have provided evidence of its efficacy on bone manifestations. In Study GZGD00304, a Phase 2 open label study, 56% (n = 10) of the patients had reduced bone marrow infiltration of the femur as assessed by MRI after 4 years of treatment with eliglustat, and the mean lumbar spine BMD (g/cm²) increased by 9.9% (n = 15, p = 0.0176). The mean standard deviation (SD) lumbar spine BMD T-score was in the osteopenic range at baseline, -1.63 (1.07), and reached the normal range, -0.88 (1.26), after 4 years of treatment (p = 0.0139). The mean (SD) lumbar spine BMD Z-score was -1.17 (0.92) at baseline and increased to -0.48 (1.07) after 4 years of treatment (p = 0.0044) (GZGD00304: 48-month period clinical study report).

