In the Pivotal Phase 3 Study GZGD02507 where patients were randomized to eliglustat or placebo, the total bone marrow infiltration score, as assessed by MRI in lumbar spine and femur, decreased by a mean of 1.1 point after 9 months (n = 20) and 2.15 points after 18 months (n = 18) in the eliglustat group. The percentage of eliglustat treated patients with a clinically significant reduction of at least 2 points in the total bone marrow infiltration score increased from 26% (n = 5) after 9 months to 44% (n = 8) after 18 months. After 18 months of eliglustat treatment the mean (SD) lumbar spine BMD T score increased from -1.06 (0.82) (n = 17), within the osteopenic range, to -0.91 (0.88) (n = 15), within the normal range. Statistically significant reductions in plasma MIP-1 β , which is considered to be a biomarker of active bone disease, were observed with eliglustat compared with placebo (least squares [LS] mean treatment difference = -43.5%, p<0.0001). After 18 months and 30 months of treatment, BMB score had decreased by a mean of 2.2 points (n=18) and 2.7 (n=15) points, respectively, for the patients originally randomized to eliglustat, compared to a mean decrease of 1 point (n=20) and 0.8 (n=16) in those originally randomized to placebo, and the percentage of eliglustat-treated patients with a significant reduction of at least 2 points in the total BMB score increased to 44% (n=8). After 18 and 30 months of treatment with eliglustat in an open-label extension phase, the mean lumbar spine Z-score in all patients increased from -1.208 (1.0546) at Baseline (n=38) to -0.949 (1.1447) (n=31). After 30 months and 4.5 years, the Z score further increased to -0.761 (1.0760) (n=31) and -0.478 (0.7870) (n=9), respectively (GZGD02507: 39-week [primary analysis period] and 78-week clinical study reports).

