11.4.2 Analyses of efficacy endpoints

11.4.2.1 Analysis of primary efficacy endpoint(s)

Five common skeletal manifestations of Gaucher disease will be summarized separately. A single composite endpoint will not be constructed.

1. Mobility, bone crisis and pain: Category of mobility status and bone pain, as well as number of new bone crises, will be summarized. Additionally shifts in category of mobility and pain from study and eliglustat baseline will be presented.
2. Bone marrow infiltration: Bone marrow infiltration score will be summarized both continuously and categorically. Reported values and changes from study and eliglustat baseline will be summarized as data is available.

Category of infiltration score will be constructed and summarized:

Mild: 0 to 4

Moderate: 5 to 8

Severe: 9-16

Shifts in category from study and eliglustat baseline will be summarized.

1. BMD: Bone mineral density in (g/cm²), as well as T and Z scores, will be summarized by time point as well as absolute and percent changes from study and eliglustat baseline.
2. Lytic lesions, fractures, infarctions and osteonecrosis. Incidence of new or worsening lytic lesions, new or worsening AVN, new or worsening infarctions and new fractures will be summarized at the 2 year and end of study time points. Annual incidence rates may also be calculated and summarized.
3. Bone biomarkers: Levels of P1NP, CTx and MIP 1 β , as well as absolute and percent changes from study or eliglustat baseline will be summarized.

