#### *2.1.3.1.3 Bone mineral density (BMD)*

BMD will be measured by DXA of both hips and the lumbar spine. T and Z scores, and bone mineral densities will be provided by the DXA report.

Centrally reviewed DXA data will be used to determine each patient's bone density category:

T-score Bone Density Categories:

- Normal: T-score  $> -1$
- Osteopenia:  $-2.5 < \text{T-score} \leq -1$
- Osteoporosis:  $\text{T-score} \leq 2.5$

Z-score Bone Density Categories:

- Normal: Z-score  $> -2$
- Below Normal: Z-score  $\leq -2$

Bone mineral density will be measured at screening and then yearly.

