##### **2.4.4.1.2 Bone marrow infiltration**

Bone marrow infiltration score by location and total bone marrow infiltration score will be summarized both continuously and categorically. Absolute values, change and percent change from baseline (study baseline and eliglustat baseline) will be summarized by visit. Category of total infiltration score (Mild: 0 to 4; Moderate: 5 to 8; Severe: 9-16) will be constructed and summarized by visit. Shifts in category of infiltration from study and eliglustat baseline will be summarized by each post-baseline visit.

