#### **2.4.4.1.3 BMD**

Absolute value, change and percent change from baseline (study baseline and eliglustat baseline) for bone mineral density in (g/cm^2), T and Z scores by location will be summarized by visit. Shift in bone density categories of T and Z scores will be summarized by visit. In addition, mean plots of absolute values and percent change from baseline for total BMD, T-scores, and Z-scores for all patients with standard deviation will be provided.

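### Two sets of SAP categories do not partition their scales: three-reader bone marrow burden averages of 4.33, 4.67, 8.33 and 8.67 have no category, and osteoporosis is printed as T-score ≤ 2.5

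*SAP*

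**What the plan says.** **BMB.** SAP 2.1.3.1.2 defines the total as the sum of seven item scores: "BMB scores range from 0 to 16 and will only be calculated for patients who have non-missing values for all seven scores". Two readers score each scan. If they differ by one point or more, a third reads it, and "The average of the three reader results will be used in the analysis". SAP 2.4.4.1.2 then states: "Category of total infiltration score (Mild: 0 to 4; Moderate: 5 to 8; Severe: 9-16) will be constructed and summarized by visit". The same section asks for shifts in category from both the study baseline and the eliglustat baseline at each post-baseline visit. Protocol 11.4.2.1 lists the same three integer bands under "Category of infiltration score will be constructed and summarized".

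**BMD.** SAP 2.1.3.1.3 says "Centrally reviewed DXA data will be used to determine each patient's bone density category". It lists Normal as T > -1, Osteopenia as -2.5 < T ≤ -1, and Osteoporosis as T ≤ 2.5, with no minus sign on the last. SAP 2.4.4.1.3 uses these categories: "Shift in bone density categories of T and Z scores will be summarized by visit".

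**The concern.** A category set for a shift table must place every possible value in exactly one class. Neither set does.

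The BMB bands suit a single reader's integer total, but the analysed value after adjudication is a multiple of one third. Values between 4 and 5, or between 8 and 9, have no class. SAP 2.5.1 to 2.5.3 (data handling and missing data) give no rounding or boundary rule. The T-score set has the opposite fault: as printed, its classes overlap.

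BMB and BMD are two of the five components of the primary endpoint, and the study is purely descriptive, so the tables are its result. Without a written BMB rule, a programmer must choose one, possibly with open-label data in view, or leave the category blank. A blank treated as missing drops out of the percentage denominator under SAP 2.5.3. With about 32 patients (SAP 1.3), one patient is 1/32, or about 3 percentage points.

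**Working it through.** **1. Score range.** Item maxima from SAP 2.1.3.1.2:
- Spine: 3 (T1) + 2 (T2) + 2 (pattern) + 1 (fat) = 8
- Femur: 2 (T1) + 3 (T2) + 3 (sites) = 8
- Total: 8 + 8 = 16

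This reproduces the stated range of 0 to 16. A single reader's total is an integer.

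**2. Possible averages.** Mean = (a + b + c)/3, with a, b and c integers from 0 to 16. The sum runs from 0 to 48, giving 49 possible means, of which 17 are integers and 32 are not. A mean has no category when it lies strictly between 4 and 5 or strictly between 8 and 9:
- Sums 13 and 14: 13/3 = 4.33 and 14/3 = 4.67
- Sums 25 and 26: 25/3 = 8.33 and 26/3 = 8.67

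So 4 of the 49 means (4 of the 32 non-integer means) are unclassified. The same four remain if the first two totals are required to differ.

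**3. How a gap arises.**

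| Primary totals | Third read | Mean | Category |
|---|---|---|---|
| 4, 5 | 3 | 4.00 | Mild |
| 4, 5 | 4 | 4.33 | none |
| 4, 5 | 5 | 4.67 | none |
| 4, 5 | 6 | 5.00 | Moderate |
| 8, 9 | 8 | 8.33 | none |
| 8, 9 | 9 | 8.67 | none |

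Wider splits can also reach a gap: totals of 3 and 6 with a third read of 4 or 5, or 7 and 10 with a third read of 8 or 9.

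**4. The choice of rule changes the category.**

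| Rule | 4.33 | 4.67 | 8.33 | 8.67 |
|---|---|---|---|---|
| Nearest integer | Mild | Moderate | Moderate | Severe |
| Round down | Mild | Mild | Moderate | Moderate |
| Round up | Moderate | Moderate | Severe | Severe |

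**5. T-score categories as printed.**
- T ≤ -2.5: osteoporosis only
- -2.5 < T ≤ -1: osteopenia and osteoporosis
- -1 < T ≤ 2.5: normal and osteoporosis
- T > 2.5: normal only

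Protocol section 4 uses the terms differently. For the Phase 2 study it says the mean "lumbar spine BMD T-score was in the osteopenic range at baseline, -1.63 (1.07), and reached the normal range, -0.88 (1.26"). For GZGD02507 it says "lumbar spine BMD T score increased from -1.06 (0.82) (n = 17), within the osteopenic range", and it calls -0.91 normal. Under the printed line all four means would also be osteoporosis. With the cut at -2.5, every T-score falls in exactly one category. The Z-score categories (> -2 and ≤ -2) already do so.

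**6. Frequency of BMB gaps (illustration only).** The documents give no reader-agreement data. An illustrative simulation of 200,000 scans assumed:
- a mean score of 3 to 9 and an SD of about 3 to 3.5;
- a 1% to 15% chance of a one-point error per item per reader;
- a third read on any item difference;
- the same true score at both visits.

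A third read was then needed for 9% to 78% of scans. Between 1.3% and 10.9% of scans had no category, and 2.5% to 18.7% of patients lacked one at either of two visits. For 32 scans at a visit, 32 × 0.013 = 0.4 and 32 × 0.109 = 3.5 unclassified.

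**The case against.** The strongest reply is that little depends on this. The study is single-arm and descriptive, and no hypothesis is tested (SAP 2.4.4). BMB is also summarised continuously, by location and in total, against both baselines. A few shift-table cells would not alter a conclusion. Four of 49 is a count of arithmetic outcomes, not a rate. The simulated percentages rest wholly on assumptions, and their upper end needs a third read on about 78% of scans. All of that stands and limits the weight of the point. It does not supply the missing rule.

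On the T-score, the lost sign could come from text extraction, and the adjacent osteopenia line makes the intended boundary plain. That is fair, and it is why the PDF should be checked first. Against it, the other three T-score bounds and both Z-score bounds in the same list keep their minus signs. The four Protocol means illustrate the overlap. They are group means from earlier studies and do not measure its effect on patients here.

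The adjudication trigger is itself ambiguous, because it lists questions, subtotals and the overall score together. If a difference at every level were required, some discordant pairs would get no third read and would have no stated rule. Using a two-reader mean for them would add 4.5 and 8.5 to the gaps.

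**Conclusion.** Both parts hold and should be fixed before database lock. The BMB gap is exact: four attainable averages have no category, and a one-point split at 4/5 or 8/9 produces one whenever the adjudicator sides with either reader. This assumes only integer totals per reader and the averaging rule as written. The T-score overlap covers every value above -2.5 and up to 2.5, provided the PDF prints the line as it appears in the text. It is then very probably a one-character error.

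The effect is confined to the categorical and shift tables for these two components. The number of patients affected cannot be derived from the documents; the simulated range is an illustration and should not be quoted as an estimate.

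**What to change.** 1. In SAP 2.4.4.1.2, define the categories on the averaged score with contiguous cut-points that reproduce the Protocol's bands on integers. Rounding to the nearest integer gives Mild < 4.5, Moderate 4.5 to < 8.5, Severe ≥ 8.5. Cutting at < 5 and < 9 is also contiguous but classifies 4.67 and 8.67 differently. Either is workable if fixed in advance and used for both the two-year and the final analysis.
2. In SAP 2.1.3.1.3, check the osteoporosis line against the source PDF. If it is printed as shown, correct it to T-score ≤ -2.5, the lower bound of the SAP's own osteopenia category.

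The cost is two lines of SAP text. No new data are needed and the continuous analyses do not change.
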